5. The vaccine recipient will receive the recommended routine childhood vaccinations, except polio vaccination. Routine polio vaccines will be replaced by the study vaccine.
6. Schedule the next visit.

Study Clinic Visit – 14 weeks of age [All arms]

During this visit, the following procedures will be conducted:

1. The medical officer will complete the eCRF and examine the vaccine recipient.
2. One blood specimen (1 ml) will be collected by venipuncture.
3. Study vaccines will be administered, as directed by study arm.
4. The vaccine recipient will be observed for 30 minutes to monitor for any adverse reactions to the study vaccine.
5. The vaccine recipient will receive the recommended routine childhood vaccinations, except polio vaccination. Routine polio vaccines will be replaced by the study vaccine.
6. Schedule the next visit.

Study Clinic Visit – 18 weeks of age [All arms]

During this visit, the following procedures will be conducted:

1. The medical officer will complete the eCRF and examine the vaccine recipient.
2. One blood specimen (1 ml) will be collected by venipuncture.
3. Completion of study activities.
4. Vaccine recipients in Arms A and B will be given the first of three bOPV doses. Note: Arm B will be given three doses of bOPV to account for possible immunologic interference during co-administration of bOPV with nOPV2. All vaccine recipients will be given the first of two fIPV doses.

Timing of Evaluations

Entry/eligibility evaluations

- Entry evaluations will be completed at 6 weeks of age.
- Blood collection and study vaccine administration are planned during the study entry evaluation at 6 weeks of age. Blood will be collected before administration of any study vaccines. On the date of enrolment, study vaccines will be administered only if adequate blood specimen has been collected. If blood cannot be collected on the day of enrolment, study vaccine recipients will be discontinued from the study.
- The window for entry evaluation including collection of blood and administration of vaccine is 42–48 days of age.

Post-entry evaluations and follow-up

- After the first enrolment visit (6 weeks of age, range 42–48 days), the window for study visits is +/- 3 days.
- Blood will be collected before any study or EPI vaccines are administered.
- Stool collection from vaccine recipients and one sibling each will take place at 8 and 10 weeks of age for all Arms, and additionally at 7 weeks for Arm A only.

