Vaccine recipients will be enrolled at 6 weeks of age. Enrolment at this early age is required because the study is assessing the immunogenicity of poliovirus vaccines that are routinely administered at this age. The current schedule for polio immunization in Bangladesh includes three doses of bOPV administered at 6, 10 and 14 weeks of age plus two fractional IPV (fIPV) ID doses administered at 6 and 14 weeks of age. Delaying vaccine recipient enrolment until they are older will not allow assessing the immunogenicity of alternative polio vaccines and vaccination schedules because most vaccine recipients will be immune as a result of the polio vaccines they received through routine immunization.

Potential Benefits and Compensation to Vaccine recipients

Vaccine recipients will receive all non-polio routine immunizations (BCG, Penta, PCV) as per the routine immunization schedule of Bangladesh. After completion of study activities, vaccine recipients in Arms A and B will receive three doses of bOPV. The three doses of bOPV will be given in 4-week intervals

beginning at 18 weeks of age. All vaccine recipients will also receive two doses of fIPV. The routine polio immunization schedule in Bangladesh is three doses of bOPV along with two doses of fIPV. During study visits, vaccine recipients will be examined by medical officers and their growth and development will be assessed. In addition, vaccine recipients and siblings will be offered advice on diagnosis and treatment of any other illnesses they experience during the study period at no cost.

For the larger public health community, the results of this clinical trial may be used to inform outbreak response vaccination strategies.

Risks to Vaccine recipients and Siblings

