bOPV has a long safety record and is used for routine childhood immunization in Bangladesh; nOPV2 is similar to mOPV2 except that it has further attenuated type 2 poliovirus. mOPV2 has been used in a polio vaccine trial by icddr,b in 2015–2016. Compared to mOPV2 and other existing OPVs, nOPV2 has been developed to be more genetically stable and therefore less likely to revert to neurovirulence. Phase 1 clinical trials of nOPV2 in IPV-primed adults demonstrated the safety of both vaccine candidates [14]. For both, viral shedding appeared to be no greater than mOPV2, and possibly lower. Mouse neurovirulence testing of shed virus also demonstrated the stability of the shed virus and deep sequencing of the shed virus revealed no unexpected mutations or loss of key stabilizing mutations, which implies a decreased likelihood of transmission of a virus with neurovirulent phenotype, relative to Sabin 2. Preliminary results from phase 2 trials in Belgium and Panama were reviewed by an independent data safety monitoring board, which supported age group progression from adults to toddlers and infants based on the available safety information. Early trial results also suggest that both candidates are immunogenic and more genetically stable than Sabin 2 [16]. Prior to the start of the current study, icddr,b will implement an OPV-naïve infants trial in Matlab that includes nOPV2 (PR-20001).

Vaccine recipients may have less immunity to polio during the study period than similarly aged non-vaccine recipients because of the altered vaccination schedule; all vaccine recipients will receive their first dose of fIPV twelve weeks later than the EPI schedule and some vaccine recipients will receive their first dose of bOPV twelve weeks later than the EPI schedule. However, the risk of infection with WPV or cVDPV is very low in Bangladesh. The last endemic WPV case was reported in 2000, and the last imported case was reported in 2006. Furthermore, WPV type 2 and WPV type 3 have been declared globally eradicated. No cVDPV cases have ever been reported in Bangladesh thanks to the high coverage reached with routine immunization since WPV elimination.

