The most significant adverse event associated with OPV is vaccine-associated paralytic poliomyelitis (VAPP); however, the risk for recipient VAPP and contact VAPP is very small as the children will be protected by maternal antibodies. The risk of VAPP is about 1 case per 1.2 to 2.4 million doses of tOPV [3]; the risk after bOPV is expected to be similar or slightly higher than tOPV for recipient VAPP as most were related to types 1 or 3 [4-6]. Because bOPV is given as part of the EPI schedule in Bangladesh, study vaccine recipients will have similar risk for developing VAPP to types 1 and 3 as infants not participating in the study. There may also be some risk of VAPP in close contacts of vaccine recipients, including the older siblings, but we assume this risk to be minimal in Bangladesh as Bangladesh has high routine immunization coverage and nOPV2 has been designed with the intent to be much less prone to reversion to neurovirulence compared to Sabin OPV.

Upon completion of study activities, vaccine recipients in the nOPV2-only arm will not have protection against types 1 and 3 and vaccine recipients in the bOPV-only arm will not have protection against type 2 until they receive their first dose of fIPV (and bOPV, depending on the arm) at 18 weeks of age.

In summary, because of protection conferred by the nOPV2 and bOPV doses provided by the study, the genetic stability of nOPV2, and the low probability of poliovirus circulation in Bangladesh during the study implementation, the risk of paralysis caused by WPV, cVDPV or OPV in study vaccine recipients, will be very low and similar or only slightly different than the risk of non-vaccine recipient infants of similar age.

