Name and signature of medical officer: _____

Clinic Visit at 18 weeks of AgeDate of visit (dd/mm/yy): / / **Clinical History**

1. Is the child currently breastfed? No breastfeeding / Partial breastfeeding / Exclusive breastfeeding
2. Has the child received any vaccine since last visit? Yes / No 2a. If yes, specify: _____
2b. Date of vaccination (dd/mm/yy): / /
3. Has any other child in the household received OPV since the last clinic visit? Yes / No 3a. If yes, specify: _____
4. Has the child had diarrhea in the last 24 hours (≥ 3 loose stools in 24 hours)? Yes / No
4a. If yes, specify: duration of diarrhea in days:
(If the child currently has fever $>38.3^{\circ}\text{C}$, blood in stools, vomiting or signs of dehydration, do not continue with study procedures. Provide advice and referral as required.)
5. Has the child been sick since the last study visit? Yes / No 5a. If yes, specify: _____
6. Is the child on any immunosuppressive medications? Yes / No 6a. If yes, specify _____

Physical Exam

7. Temperature: . $^{\circ}\text{Celsius}$
8. Length #1: . cm
9. Length #2: . cm
10. Weight #1: . kg
11. Weight #2: . kg

Blood Collection

12. Blood sample collected? Yes / No 12a. If not, why? _____
13. Sufficient quantity (1 ml)? Yes / No 13a. If insufficient, why? _____
14. Time of collection (hh:mm): :

Schedule next visit date to begin routine polio vaccination schedule (dd/mm/yy): / /

Name and signature of medical officer: _____

Adverse Event Form**Date of report (dd/mm/yy):** / / **Report Status:** Initial Report Follow-up Report Final reportInitials of parent providing information: Vaccine recipient date of birth (dd/mm/yy): / / **Description of the event**Is this a solicited (from the 24–48 hours after 6-week vaccination) or unsolicited AE? **Solicited / Unsolicited****Date of onset (dd/mm/yy):** / / **Time of onset (hh:mm):** :

Describe briefly relevant clinical symptoms and signs: _____

Results of diagnostic tests performed: _____

Medications prescribed: _____

Diagnosis (circle: Current / Final): _____**Severity (circle what applies):** Mild / Moderate / Severe**Did any of the following occur or are present? (if present, report immediately as a Serious Adverse Event)**

Paralysis, severe disability or incapacity, or substantial

disruption of the ability to conduct normal functions Yes / No

Anaphylaxis Yes / No

Hospitalization or prolongation of existing hospitalization Yes / No

Death Yes / No

Life-threatening event Yes / No

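### The 18-week form in Appendix A books a later visit to start polio vaccination, whereas the protocol body gives the first catch-up doses at the 18-week visit itself (minor inconsistency)

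*Protocol*

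**What the plan says.** In the protocol body, the section *Study Clinic Visit – 18 weeks of age* lists four procedures. The first three are examination, a 1 ml blood sample and the end of study activities. The fourth is the start of catch-up vaccination: "Vaccine recipients in Arms A and B will be given the first of three bOPV doses", and "All vaccine recipients will be given the first of two fIPV doses".

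The ethics sections fit this timing. *Potential Benefits and Compensation to Vaccine recipients* says "The three doses of bOPV will be given in 4-week intervals" and starts that series at 18 weeks of age. *Risks to Vaccine recipients and Siblings* says "all vaccine recipients will receive their first dose of fIPV twelve weeks later than the EPI schedule". The same section states that "vaccine recipients in the nOPV2-only arm will not have protection against types 1 and 3", and that the bOPV-only arm lacks type 2 protection, "until they receive their first dose of fIPV (and bOPV, depending on the arm) at 18 weeks of age".

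The form *Clinic Visit at 18 weeks of Age* in Appendix A has 14 items: clinical history, physical examination and blood collection. Item 14 is the time of the blood draw. The only line between it and the medical officer's signature is "Schedule next visit date to begin routine polio vaccination schedule".

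**The concern.** The body starts the catch-up series at the 18-week visit, and the form books a further visit at which to start it. A reader holding both cannot tell from the form which is meant.

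What is at stake is participant protection. Under the study schedule Arm A has had no vaccine against types 1 and 3, and Arm C none against type 2. The risk section accepts these gaps on the footing that they close at 18 weeks. A member of staff who followed the printed form would let them run on. Arm B has received all three types, so there only the precautionary repeat bOPV and the fIPV would be late.

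The form matters in practice. *Records to be kept* has clinic data entered in REDCap, but it keeps paper case report forms as back-up and switches to them if the tablet system fails.

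**Working it through.** The protocol gives no sample size, power or error-rate figure on this point. The check is a comparison of texts, with one sum.

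**1. Do the body statements agree with each other?**
- Visit procedures: first bOPV (Arms A and B) and first fIPV (all arms) at the 18-week visit.
- Benefits section: bOPV series starts at 18 weeks.
- Risk section: first fIPV twelve weeks behind the national schedule. *Justification for Involving a Vulnerable Population* puts the first routine fIPV dose at 6 weeks, so 6 + 12 = 18 weeks.
- Risk section: the unprotected period ends at 18 weeks.

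All four fit. Only the first names the visit; the others give an age or a lag.

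**2. Does the form agree with them?**
- The 6-, 10- and 14-week forms each have a vaccine administration section, which also records routine non-study vaccines (pentavalent and PCV), and a 30-minute observation item.
- The 18-week form has neither.
- The 14-week form closes with a plain instruction to schedule the next visit. The 18-week form adds the purpose of that visit, which is to begin polio vaccination. The wording is therefore specific to this form and was not carried over from the others.
- The line makes no distinction by arm, although Arm C is due no catch-up bOPV.

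Read on its own, the form places the first dose at a visit after the 18-week visit. The body places it at the 18-week visit.

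**3. How long would the delay be?**
The form states no interval. Two figures elsewhere might be borrowed, but neither applies. In *Post-entry evaluations and follow-up*, "the window for study visits is +/- 3 days" concerns study visits, and a vaccination visit after the end of study activities is not clearly one. The 4-week interval in the benefits section lies between bOPV doses, not before the first. The size of the delay is therefore unknown.

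**4. Who could be affected?**
By enrolment target, first bOPV would be late in Arms A and B (265 + 265 = 530 infants) and first fIPV in all arms (3 × 265 = 795). These are upper limits before attrition, and they assume that the printed line is followed throughout.

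**5. Does it reach the analysis?**
No. *Post-entry evaluations and follow-up* requires blood to be taken before any study or routine vaccine. The 18-week titres are the same whether the catch-up doses follow on that day or later.

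**The case against.** The strongest reply is that one line on a data form stands against four consistent statements in the body. Staff are to be trained on operating procedures (*Site Monitoring Plan*), monitors are to check compliance with the protocol, and the working instrument is a REDCap screen that nobody outside the trial can see. The Adverse Event Form in Appendix A also has an 18-week row for routine vaccines, so the form set allows for vaccination at that visit. These points stand, and they make an actual delay less likely. They do not remove the conflict. The operating procedures are not shown, and the Adverse Event Form is filled in only when an event is reported.

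Four stronger readings are tempting, and the documents do not support them.
- *The two instructions are wholly incompatible.* Staff can give the doses after the blood draw and still book a next visit. Only the stated purpose of that visit, to begin vaccination, conflicts.
- *The absence of bOPV and fIPV fields is itself an error.* No section requires a study form to record doses given once study activities are complete, and leaving them off may be deliberate. The absence matters only because, with the last line, it leaves the form without a step for the doses.
- *First doses would be late by a definite number of days or weeks.* No section gives an interval before the first catch-up dose.
- *Parents were told one age and infants vaccinated at another.* The 18-week statement cited here is in the protocol's risk section. The consent pages are not available, so what parents were told is unknown.

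**Conclusion.** The inconsistency holds and is minor. The body gives the first catch-up bOPV (Arms A and B) and the first fIPV (all arms) at the 18-week visit. The last line of the 18-week form books a later visit to begin that schedule, and the form has no step for the doses.

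The consequence depends on staff following the form as printed. In that case first doses would come after 18 weeks by an interval that the protocol does not state. The risk section describes the chance of infection with wild or circulating vaccine-derived poliovirus in Bangladesh as very low, which limits the seriousness. Objectives, endpoints, sample size and analysis are untouched. The mismatch in the text is certain; that any infant would be vaccinated late is not.

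**What to change.** Keep the timing in the body. On the 18-week form, replace the last line with one that does two things:
- confirms that the first catch-up doses were given at this visit, after the blood draw (bOPV and fIPV in Arms A and B, fIPV in Arm C);
- books the next catch-up dose due by arm. For Arms A and B the next bOPV falls four weeks later, at 18 + 4 = 22 weeks. For Arm C only the second fIPV remains. The sections shown give no interval for the second catch-up fIPV dose, so its date should be taken from the operating procedures or the national schedule.

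Check the REDCap screen for the same line and change it to match. Separate administration fields for bOPV and fIPV, in the style of the earlier forms, are optional.

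The cost is one edit to a form and one check of a screen. Nothing in the design or the analysis changes.

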Appendix B: Microneutralization Test for Polio Antibodies

Prepared by	Date Adopted	Supersedes Procedure
[name]	4/2/2014	12_10_10

Introduction

The polio microneutralization assay measures neutralizing antibody titers to poliovirus types 1, 2, and 3 using 96-well microtiter plates (it is termed “microneutralization” because the original neutralization assay was performed using larger volumes on culture tubes). The principle of the test is that the anti-poliovirus antibodies in a serum sample will bind to the virus and block infection of susceptible cells. Because poliovirus is cytopathic, virus that is not bound by antibody infects and lyses cells. The amount of neutralizing antibody is quantitated as a 50% endpoint titer; that is, the dilution of serum that protects 50% of susceptible cells from poliovirus infection and cytopathic effect.

The test takes approximately seven days to complete, from the dilution of sera to staining and reading plates, and data analysis. Each test serum is run in triplicate and diluted from 1:8 to 1:1024; a single 96-well plate contains four test sera (Figure 1). This test may be performed manually, automated, or in a combination of the two approaches (Figure 2). For large studies, automation is recommended.

[figure not shown]

Figure 1. 96-well plate setup for Polio Serology

For a single run, up to 96 sera, which fit on 72 plates (24 plates per serotype), can be tested. For most purposes, the Sabin vaccine strains are used, but other poliovirus strains can be used. Control plates are generated for each run and consist of three back titration plates with no antibody added (one for each Sabin virus) and a cell control plate (no virus or antibody added, to assess cell viability). At the end of each run, control plates are checked for accurate dilution of each Sabin poliovirus (back titration plates) or cell monolayer confluence (cell control plate).

If more than seven sera are being tested, the samples must be randomized using a balanced block randomization scheme with integrated controls. Included in each run is a control serum designated In-House Reference Serum (IHSR), which is pooled from serum samples with high neutralizing antibody titers to each Sabin poliovirus.

The IHRs is tested in multiple replicates, on multiple plates in each run, to provide a measure of assay variability within a run.

[figure not shown]

Figure 2. Workflow for automated poliovirus microneutralization assay

Materials and Equipment

Most of these items may be substituted with equivalent items from other manufacturers/suppliers but alternative materials must be validated against an appropriate standard.

Consumables

- T-150 tissue culture flasks (Corning, #430823)
- 96-well tissue culture, clear, sterile plates (Corning, #3997)

- Low evaporation lids (Corning, #3931)
- 96-well tissue culture, clear, sterile, (Corning #3997)
- Plastic wrap (e.g., Saran Wrap)
- Deep-well 96-well microplate, 2.2 ml capacity. (VWR, #40002-014)
- Mat lids for 2.0 mL microplates (VWR, #400002-018)
- Sterile pipettes; 10 ml, 25 ml (Falcon, #357551, #357325)
- Single-channel pipettes:
 - Manual: LTS 20, 200, 1000 (Rainin)
 - Electronic: 10-300, 50-1000 (Biohit)
- 12-channel pipettes
 - Electronic: 10-300, 50-1200 (Biohit)
- Pipette tips
 - Rainin: RT-L200F, RT-L1000F, RT-L10F
 - Biohit: 350 µL, 1000 µL, 1200 µL
- WellPro 250 µL sterile pipette tips (ProGroup)

Cells and Media

- HEp-2C cells (ATCC # CCL23)
- Cell culture media
 - Eagle's Minimum Essential Media (EMEM)(Gibco, #11095-072)
 - Penicillin/streptomycin (Gibco, #15140)
 - Fetal Bovine Serum - Optima (Atlanta Biologicals, #S12450)
 - 0.05% Trypsin-EDTA (Gibco, #25300)
- Nalgene 500 mL, 0.20 µm filter (Nalgene, #450-0020)

Antigens and Control Sera

- In House Reference Sera (developed in-house)(See Note 1.4.4)
- Sabin virus stocks grown in HEp2-C cells

Staining

- Crystal violet stain (0.05% crystal violet, 0.5% Tween-20, 50% ethanol, in H₂O)

To prepare crystal violet stock solution:

2 g	crystal violet (Sigma, C-3386)
1000 ml	95% ethanol

Mix together overnight, with stirring, until dissolved; may be stored up to one year at room temperature

To prepare working dilution crystal violet solution:

250 ml	crystal violet stock solution
5 ml	Tween-20 (Fisher Scientific, #BP337-100)
750 ml	deionized H ₂ O

Equipment and Automation

- CO₂ water-jacketed incubator (ThermoFisher Model 3110 or equivalent)
- WellPro 4000 CE (ProGroup)
- EL406 plate washer and dispenser (BioTek)

- MicroFlo dispenser (BioTek)
- Evo 100 (Tecan)
- TC20 Automatic Cell Counter (BioRad)
- PerkinElmer Victor X4 Multimode plate reader or equivalent

Protocol

In the week preceding the test runs:

1. Assign sera randomly to each run using a balanced block randomization scheme (see Note 3).
2. Use the list generated by the randomization scheme to label plates and organize sera to be tested. Each test serum is run in triplicate, so four sera may be run on each plate (Figure 1). Each plate is duplicated two more times, yielding three plates, one for each poliovirus serotype. There will also be a back-titration plate for each serotype, and one cell control plate per run.
3. In this example of a randomized sample list (Table 1), serum sample number 0000000001 will be in run number 420, position 4 on plates 5 (PV1), 29 (PV2), and 53 (PV3). The in-house reference serum (IHRs) is in position 2 on plates 7 (PV1), 30 (PV2), and 55 (PV3).

RUN ^a	PV1 Plate ^b	PV2 Plate ^b	PV3 Plate ^b	Position ^c	Sample ID ^d
420	5	28	53	1	0000000001
420	5	28	53	2	0000000002
420	5	28	53	3	0000000006
420	5	28	53	4	0000000009
420	6	29	54	1	0000000011
420	6	29	54	2	0000000030
420	6	29	54	3	0000000025
420	6	29	54	4	0000000041
420	7	30	55	1	0000000013
420	7	30	55	2	IHRs
420	7	30	55	3	0000000038
420	7	30	55	4	0000000051

Table 1. Example of randomized sample list for poliovirus microneutralization assay.

^a each run of 1-96 sera

^b PV1, polio type 1; PV2, polio type 2; PV3, polio type 3

^c see Figure 1

^d unique specimen ID

4. For each run, the IHRs is tested an average of 4-6 times, depending on the number of samples being randomized (see Note 4).
5. The labelling of the assay plates should reflect the setup of the serology run reflected in the randomized list. A suggested plate labelling scheme is shown in Figure 3.

[figure not shown]

Figure 3. Suggested labeling scheme for assay plates.

6. Prepare MEM+ 2% FBS and MEM+10% FBS:

- FBS must be inactivated at 56°C for 30 minutes and filtered with a Nalgene 0.2 µm filter
- Add 1 mL of streptomycin/penicillin to 1000 mL of EMEM (0.1%)
- Add 20 ml (2%) or 100 mL (10%) of fetal bovine serum to 1000 ml bottle of EMEM
- MEM+10% FBS is used for maintaining HEp2-C cells and generating the cell suspension.
- MEM+2% FBS is used for filling the assay plates, diluting sera, and diluting the virus.

Prior to each test run:

- 24-48 hours before each run, seed T-150 flasks with 30 ml of HEp2-C cells at 5×10^5 cells/ml.
 - Approximately 3-4 flasks are needed for one run of 96 sera
- Incubate flasks at 37°C, 5% CO₂, in a humidified atmosphere for 24 to 48 hours to ensure that cell monolayers are confluent the day assay runs are started.

OPTIONAL - One day before test run:

The following steps can be done the day of the run or the day before the addition of the virus.

- Manually aliquot 100 µl of each serum sample into deep-well polypropylene microplate, sealed with a mat lid, and heat inactivated at 56°C in a water bath for 30 minutes.
- Store at 4°C until ready to generate the triplicate sample plates (no more than 24 hours).
- Prepare IHRS for testing (See Note 4)
- Use a multichannel pipette to add 300 µl MEM+2% FBS to 100 µl heat-inactivated test serum aliquots (for a final dilution of 1:4)
- For a full run (i.e. 96 sera), label two stacks of 12 microplates for each serotype (Figure 3).
 - Use a lidded microplate for the top of each stack, with the low evaporation lid
 - The 11 remaining microplates can be lidded or lidless; removal of lids is required for many automation systems
 - Cell control and back titration plates can be set up in lidded plates

AUTOMATED

A6. Use the MicroFlo reagent dispenser program “MEDIA 25UL” to add 25 μ L MEM 2% FBS to the test plates.

[figure not shown]
- This program adds 25 μ L MEM+2% FBS to all wells for each test plate and the back titration plates (PV1, PV2, and PV3).
- For the cell control plate, a total of 50 μ L MEM+2% FBS should be added to each well. This plate can be filled twice using the “MEDIA 25UL” program.

A7. Use the TECAN programs “1 or 2 plate triplicate transfer” to make triplicate sample plates (Figures 4A).

- This program will transfer 100 μ L of test serum in a deep-well plate (from Step 3) in triplicate to a triplicate sample plate.

A8. Using electronic single-channel pipette, transfer 25 μ L of test serum from triplicate sample plate (Step 6) to three different test plates (one for each serotype) (Figure 4B).

A

B

[figure not shown]

Figure 4. . For each run, 100 μ L of sample is transferred from sample plate to dilution plates in triplicate (enough for starting three 25 μ L sample dilutions) (A). For simplicity, only the first 8 samples are shown in the deep 96-well plate. The TECAN configuration will allow for triplicates in consecutive order. This step can transfer 96 samples from one 96-deep well plate to a 96-well triplicate sample plate in 22 min. (B) Using a 12-channel manual pipette, each row of from the triplicate sample plate is transferred to a test plate in triplicate for each serotype.

A9. Use the WellPro program “SD25” to perform 2-fold serial dilutions (Figure 5).

- This program will transfer 25 μ L of the diluted serum in row A to row B, then from row B to row C, etc.

- b. For row H, 25 μ L will be aspirated and discarded with the tips, to maintain the correct total volume.
- c. For each transfer, the program will mix the diluted serum a total of 4 times.
- d. Using this program will produce serum dilutions ranging from 1:8 to 1:1024.
- e. This step generates the test plates, ready for addition of virus and cells.

[figure not shown]

Figure 5. Each test serum is serially diluted (2-fold) from 1:8 to 1:1024 in triplicate. This is repeated for each test plate designated for poliovirus serotypes 1, 2, or 3.

A10. Arrange the plates in stacks of 12-13; use a lid to cover the top plate of each stack of plates and wrap in plastic Saran wrap.

A11. Plates can be stored overnight at 4°C.

MANUAL

- M5. Use electronic multichannel pipette to dispense 25 μ L MEM+2% FBS to the test plates.
 - a. Add 25 μ L MEM+2% FBS to each well of the back titration plates (PV1, PV2, and PV3).
 - b. Add 50 μ L MEM+2% FBS to each well of the cell control plate.
- M6. Use an electronic multichannel pipette to transfer 25 μ L of each test serum (from Step 3) to each test plate in triplicate (Figure 4B).
- M7. Using a multichannel pipette, make serial 2-fold dilutions from row A to row H. (serum dilution will range from 1:8 to 1:1024) (see Figure 5 for plate layout).
 - a. Discard 25 μ L from row H to make final volume for all wells 25 μ L.
- M8. Cover the top plate of each stack of plates and wrap in plastic wrap.
- M9. Plates can be stored overnight at 4°C.

Day of run:

1. Dilute each virus in MEM+2% FBS to contain 100 CCID₅₀ according to Table 2.
 - a. Prepare sufficient virus challenge suspension for the number of sera to be tested; each plate requires approximately 2.5 ml of diluted challenge virus.
2. Prepare the back titrations of each poliovirus serotype in MEM+2% FBS. Titrate each virus from 100 CCID₅₀ a further three 10-fold steps (Figure 6).

Sabin 1 (NIBSC 01/528)		100 TCID ₅₀ = 10 ^{-5.28}		10 TCID ₅₀		1 TCID ₅₀		0.1 TCID ₅₀	
Virus	100 µL	100 µL	100 µL	100 µL	100 µL	100 µL	100 µL	100 µL	100 µL
Medium	38 µL	900 µL	900 µL	900 µL	900 µL	900 µL	900 µL	900 µL	900 µL
Sabin 2 (NIBSC 01/530)									
Virus	100 µL	100 µL	100 µL	100 µL	100 µL	100 µL	100 µL	100 µL	100 µL
Medium	82 µL	900 µL	900 µL	900 µL	900 µL	900 µL	900 µL	900 µL	900 µL
Sabin 3 (NIBSC 01/532)									
Virus	100 µL	100 µL	100 µL	100 µL	100 µL	100 µL	100 µL	100 µL	100 µL
Medium	82 µL	900 µL	900 µL	900 µL	900 µL	900 µL	900 µL	900 µL	900 µL

Table 2. Example Virus Dilution for 100 TCID₅₀ and Back Titration Plate for Sabin type 1, 2, and 3

[figure not shown]

Figure 6. Layout for back titration plate. A back titration plate is made for each virus tested in the microneutralization assay.

AUTOMATED

A3. Use the MicroFlo program VIRUS 25UL to add 25 μ L of 100 CCID₅₀ of relevant poliovirus antigen to all wells in the diluted serum test plates. Use a different sterile dispensing cartridge for each virus.

MANUAL

M3. Use an electronic, multichannel pipette to add 25 μ L of 100 CCID₅₀ of relevant poliovirus antigen to all wells in the diluted test plates.

M4. Prepare back titration plate (Figure 6) for each Sabin strain using dilutions prepared in step 2 (Table 2).

- Add 25 μ L of 100 TCID₅₀ of virus to rows A and B (i.e., 24 wells/dilution)
- Add 25 μ L of the next three 10-fold dilutions to rows C and D, E and F, and G and H, respectively (See Table 2 for dilutions).
- Change pipette tips between each dilution

M5. Wrap all plates in plastic wrap and incubate for 3 hours at 35°C and 5% CO₂

M6. During serum-virus incubation, wash HEp2-C monolayer cell cultures (from 150 cm² flasks), trypsinize, and count cells using automatic cell counter (BioRad) or a hemocytometer.

M7. Prepare a cell suspension in MEM+10% FBS to contain 3 x 10⁵ cells/ml. Prepare a sufficient volume of cells: each plate requires approximately 2.5 ml of cell suspension, and every run requires 3-4 confluent 150 cm² flasks. Store cells in glass bottle at 4°C until ready to use.

AUTOMATED

A4. Use MicroFlo program “CELL 25UL” to add 25 μ L of prepared cell suspension to each well of every plate.

MANUAL

- M8. Use a repeating, multichannel pipette to add 25 μ L of prepared cell suspension to each well of every plate.
- M9. Wrap all plates in plastic wrap, in stacks of 12-13 plates. *To prevent spills and cross-contamination, avoid abrupt handling of plates.*
- M10. Carefully transfer plates to incubator for 5 days incubation at 35°C and 5% CO₂.

Plate washing and staining.

AUTOMATED

- A1. After 5 days incubation, use the Biotek EL406 to wash and stain plates with crystal violet solution.
- A2. This will aspirate wells and dispense 50 μ L of crystal violet stain (0.05%) to all wells.
- A3. Incubate for a minimum of 40 minutes at room temperature.
- A4. Run wash program
 - a. This program will aspirate the crystal violet stain then fill all wells with 250 μ L of tap water and aspirate.
 - b. This process will be repeated 3 more times to completely remove any excess crystal violet stain in the test plates prior to reading.

MANUAL

- M1. After 5 days incubation, aspirate/discard media with multichannel pipette into freshly made 0.5% sodium hypochlorite solution.
- M2. Using a repeating, multichannel pipette, add 50 μ L crystal violet stain (0.05%) to all plates.
- M3. Incubate for a minimum of 40 minutes at room temperature.
- M4. Aspirate/discard stain with multichannel pipette, fill each well with tap water (approximately 250-300 μ L), and discard.
 - a. Repeat washing step 3 more times.
- M5. Allow plates to dry at room temperature for approximately 30 minutes.
- M6. Plates should be kept at room temperature until results are calculated and results are reported.

Notes

1. Data Collection

AUTOMATED

- A1. Read plates with ELISA reader at 595 nm wavelength.
 - a. Data from plate reader can be processed using macros written in Visual Basic for Microsoft Excel.
 - b. Use an absorbance cutoff value of ≥ 0.8 as positive for neutralization (i.e., intact monolayer).
 - c. Automatically calculate the titer for each specimen using Formula 1 below (Step 2).

MANUAL

- M1. For each triplicate test serum, count the total number of wells positive for neutralization (i.e., purple wells).
- M2. To calculate titer:

Formula 1

$$\text{Titer} = (\# \text{ positive wells} / \# \text{ replicates}) + 2.5$$

- To calculate reciprocal titer:

Formula 2

$$\text{Reciprocal titer} = 2^{\text{titer}}$$

- For the neutralization titers, the upper limit of detection is 10.5 and the lower limit is 2.5, which is considered negative.

2. Cross-checking stained plates

- To ensure accuracy, each plate is cross checked to verify correct order of plates and compare plate staining pattern to electronic data file to verify titer.
- Due to the variance of the assay, there is a statistical likelihood that some wells will have virus not neutralized by antibody despite neutralization at lower serum dilutions.
- To account for this, stained plates should be checked for these situations and the data corrected according to the following guidelines (Figure 7).

[figure not shown]

Figure 7. Example of cross-checking a crystal violet stained 96-well plate for poliovirus serology assay.

Example 1

- For Test Serum 1, the reader software will automatically read this as a titer of 7.83 (1:227)
- By cross-checking the plate, we will count D1 as positive for neutralization because the 1:128 and 1:256 dilutions (E1 and F1) are positive for neutralization (i.e., purple).
- Using Formula 1, the titer is adjusted to 8.17 (1:288)

Example 2

- For Test Serum 2, the reader software will automatically read this as a titer of 6.83 (1:114)
- By cross-checking the plate, we will count F5 as negative for neutralization because the 1:64 dilutions (D4, D5, and D6) are negative for viral growth

3. Summary of Randomization Process

1. For each study, the specimen number, study site, study arm, patient number, and the unique ID for each specimen.
2. Each run needs to have 4-6 in-house reference sera.
 - a. Based on the total number of runs and the number of divisions per plate, the program will also determine how many plates will be required.
 - b. The function determines how many unique subjects exist in the file and how many unique study groups exist (where a study group is a unique combination of study site and study arm for multi-site or multi-arm studies). Each study group will be evenly represented in each run, so the program assigns the subjects within each study group randomly and evenly amongst the runs.
 - c. After each subject identifier is assigned a run number, all sera associated with those subject identifiers are assigned to the same run.
 - d. Finally, plate numbers and plate positions are randomly assigned to the sera within each run, and a spreadsheet of the randomized sera is created, in MS Excel format.
3. At the prompt, enter in the first run number for this group of serology runs.
4. At the next prompt, enter in the code that represents the first specimen per subject (for example SE1) in the input file.
5. At the next prompt, select the path and name of the output file.
6. A dialog box will appear when the process is complete.
7. Review the output to confirm that all samples were included in the randomized output.

4. In-House Reference Serum (IHRS)

1. The in-house reference serum should be established by measuring polio neutralizing antibody titers in a population of immunized subjects.
2. Multiple sera with high neutralization titers (≥ 7.5) should be pooled to generate a high-volume control.
3. Make 100 μ L aliquots of the pooled sera to be stored at -20°C for future use. Once thawed, IHRS aliquots must be stored at 4°C for no more than 3-4 days.
4. To prepare the IHRS for use in the serology assay, adjust the initial dilution such that the endpoint titer is reached on the 3-5 dilution on an assay plate.

Make the initial dilution of the IHRS and transfer to the wells that are designated for the IHRS in the randomized list (See Table 1).

